### **10.2 Visit 2- Surgery and Post-operative hospitalization**

Time of Surgery

1. Urine pregnancy test (females)
2. Open randomization allocation envelope
3. Initial analgesic application (cryoanalgesia or epidural) and Nuss procedure

According to inpatient unit protocol

1. Perform and record vital signs.
2. Perform and record oximetry.

Once per day while inpatient

1. Concomitant medications review.
2. Perform abbreviated physical examination.

Twice-per-day study visits while inpatient

1. Record any Adverse Experiences
2. Administer inpatient survey (see separate document)

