### **4 STUDY DESIGN**

#### **4.1 Study Overview**

This study is a prospective, randomized trial to compare cryoanalgesia to standard epidural analgesia for post-operative pain management in patients undergoing minimally invasive pectus excavatum repair (the Nuss procedure). Approximately 20 subjects will be randomized in 1:1 ratio to receive cryoanalgesia or epidural analgesia at the time of their procedure. Post-operative care and analgesic protocol will be identical for all patients with the exception of continuous epidural infusion (no bolus or PCEA). Upon discharge, patients will return to clinic for 4 total follow-up appointments: 2 weeks, 1 month, 3 month, and 1 year from the date of their surgery.

Screening data will be reviewed to determine subject eligibility. Subjects who meet all inclusion criteria and none of the exclusion criteria will be entered into the study.

Total duration of subject participation will be 1 year. Total duration of the study is expected to be 1.5 years.

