### **6.3 Exclusion Criteria**

- Pre-op pain medication usage
- Pectus carinatum
- Poland's syndrome or other complex chest wall anomaly
- Previous repair of Pectus Excavatum by any technique
- Previous thoracic surgery
- Congenital heart disease
- Bleeding dyscrasias
- History of previous problems with anesthesia or major anesthetic risk factors
- Pregnancy or active breastfeeding
- Non-English speaker

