### **7.1 Allowed Medications and Treatments**

Standard therapy is allowed. Patients on pain medication prior to procedure will be excluded, as stated above.

Prohibited Medications and Treatments: none

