## **10 EVALUATIONS BY VISIT**

### **10.1 Visit 1 – Pre-operative evaluation**

1. Review the study with the subject (subject's legal representative) and obtain written informed consent and HIPAA authorization and assent, if appropriate.
2. Record demographics data.
3. Record medical history, including a history of pectus excavatum and any prior treatments or procedures.
4. Record concomitant medications.
5. Perform a complete physical examination.
6. Perform and record vital signs.
7. Perform and record oximetry.
8. Perform and record results of blood pressure testing.
9. Assign unique study number for randomization

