## 13 PROTOCOL VIOLATIONS

A protocol violation occurs when the subject or investigator fails to adhere to significant protocol requirements affecting the inclusion, exclusion, subject safety and primary endpoint criteria. Protocol violations for this study include, but are not limited to, the following:

- Failure to meet inclusion/exclusion criteria
- Interference with randomization
- Non-compliance with study drug regimen

Failure to comply with Good Clinical Practice (GCP) guidelines will also result in a protocol violation. The investigator will determine if a protocol violation will result in withdrawal of a subject.

When a protocol violation occurs, it will be discussed with the investigator and a Protocol Violation Form detailing the violation will be generated. This form will be signed by a Sponsor representative and the Investigator. A copy of the form will be filed in the site's regulatory binder and in the Sponsor's files.

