### 14.1 Data Sets Analyzed

All eligible patients who are randomized into the study and receive at least the initial analgesic application (cryoanalgesia or epidural catheter placement) and undergo Nuss procedure will be included in the analysis.

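### Pain-medication eligibility is not re-checked before the envelope is opened, so a patient can be ruled ineligible with the arm already known

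*Combined protocol and SAP*

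**What the plan says.** All references are to the combined protocol and SAP.

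- **The criterion.** Section 6.3 lists pre-operative pain medication use as an exclusion. Section 7.1 ties it to the operation: "Patients on pain medication prior to procedure will be excluded, as stated above".
- **When eligibility is decided.** Section 4.1 says "Screening data will be reviewed to determine subject eligibility", and patients who satisfy every criterion are then entered.
- **When medication is looked at.** Section 10.1 (Visit 1) has the item "Record concomitant medications". In section 10.2 the numbered steps at the time of surgery are a urine pregnancy test for females, then "Open randomization allocation envelope", then the analgesic and the Nuss procedure. Medication review reappears below these steps, among the once-daily inpatient items.
- **Who knows the arm.** Section 8.1 has the envelope opened on the morning of surgery. Section 8.2 accepts that patients and clinicians are unblinded from then on, and gives prevention of selection bias as the reason for concealment until that time.
- **What follows from a failed criterion.** Section 13 counts it as a protocol violation and adds: "The investigator will determine if a protocol violation will result in withdrawal of a subject". Section 14.1 analyses "All eligible patients who are randomized into the study and receive at least the initial analgesic application" and undergo the operation. Section 12.4 rules out replacement of withdrawals.

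**The concern.** Pain-medication use can change between Visit 1 and surgery, and the protocol sets no limit on that interval. A patient who began an analgesic in between is ineligible under 7.1, yet no scheduled step would reveal this before the arm is known. When it does come to light, the decision falls to someone who knows the allocation. Section 14.1 does not fix the time at which eligibility is judged, so the judgement could even be made at analysis, with the length of stay known.

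Concealment until the morning of surgery protects the comparison only if nobody is removed on discretionary grounds afterwards. With 10 patients per arm, each removal is 10% of an arm. If removals depend on both arm and prognosis, the difference in mean stay is biased. If they do not, the trial loses some power.

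**Working it through.** **Sequence**

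| Step | Source | Pain medication checked? | Arm known? |
|---|---|---|---|
| Visit 1 history and medications; eligibility reviewed from screening data | 4.1, 10.1 | Yes | No |
| Interval to surgery, length not stated | – | No | No |
| Pregnancy test | 10.2 | No | No |
| Envelope opened | 8.1, 10.2 | No | Yes |
| Analgesic and Nuss procedure | 10.2 | No | Yes |
| Daily inpatient medication review | 10.2 | Yes | Yes |

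Appendix 1 marks medication review under Visit 2 without an order within the visit, so the placing of the last row rests on the listing in 10.2.

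**How a late finding removes a patient.** If the patient is withdrawn before the analgesic is given, the receipt condition in 14.1 drops the patient. If the finding comes later, the word eligible in 14.1 is what could drop the patient.

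**Inputs for size.** SD 1.3 days, difference 2 days, type I error 0.05, power 90% and 18 patients raised to 20 (14.5); two-tailed unpaired t test (14.3).

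**The plan's own figure.** Per arm, n = 2(z₀.₉₇₅ + z₀.₉₀)² × SD² / difference² = 2 × (1.960 + 1.282)² × 1.3² / 2² = 8.88, rounded up to 9, or 18 in total. The stated figure reproduces.

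**If removal is unrelated to length of stay.** Power comes from the noncentral t distribution with noncentrality 2 / [1.3 × √(1/n₁ + 1/n₂)]:

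- 10 v 10: noncentrality 3.44, 18 df, power 90.2%
- 10 v 9: noncentrality 3.35, 17 df, power 88.4%
- 10 v 8: power 86.1%

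**Illustrative upper bound if removal is related to stay.** Assume no true difference, normal stays with SD 1.3, 10 per arm, and removal of the longest stays from one arm only (200,000 simulated trials):

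| Removed from one arm | Mean shift in difference | Type I error |
|---|---|---|
| 0 | 0.00 days | 5.0% |
| 1 | 0.22 days | 7.5% |
| 2 | 0.41 days | 11.5% |

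As a check on the second row, dropping one value from 10 moves the mean by that value's distance from the arm mean divided by 9. A shift of 0.223 days implies a distance of 0.223 × 9 = 2.0 days, or 2.0 / 1.3 = 1.54 SD, which is plausible for the longest of 10 stays. The shift is 0.22 / 2 = 11% of the planned effect.

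**The case against.** The strongest reply is that 4.1 settles eligibility from screening data before entry, so eligible in 14.1 can naturally mean eligible at entry. On that reading a later finding changes nothing in the analysis set. This is a fair reading, but 14.1 does not state it, and section 13 treats a failed criterion as a violation that may lead to withdrawal.

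Two other provisions help only in part. Section 7 asks that medications stay the same, with no new chronic therapy, but it allows for medical need, does not cover short-term analgesic use, and is not a check. Section 13 requires a form signed by a sponsor representative as well as the investigator. That documents the violation, but the decision on withdrawal remains the investigator's.

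Three stronger readings are tempting and are not supported:

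- **Anesthetic risk.** A reader might infer that the exclusion "History of previous problems with anesthesia or major anesthetic risk factors" is examined more closely when an epidural is planned, so that late exclusions fall on that arm. The documents do not say so. The criterion has no time window, is partly a matter of history taken at Visit 1, and has no later scheduled check. Both arms have the same operation, and 8.4 has supplies for both methods ready each time. A routine anesthesia assessment may also precede the envelope, although none is scheduled.
- **Haller index.** The threshold in 6.2 is missing from the synopsis and the visit lists. However, it is a fixed measurement, and 14.2 has deformity severity recorded at screening. The mismatch is a separate editorial point with no bearing on when the envelope is opened.
- **Actual bias.** Nothing shows that such removals have occurred or would depend on the arm.

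**Conclusion.** The point stands for pain medication. The rules as written allow a patient to be removed for ineligibility by someone who knows the arm, because the only check before opening is pregnancy and 14.1 does not fix when eligibility is judged. It is an open route to bias of unknown frequency.

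The figure of about 0.22 days and 7.5% type I error for one removal is a ceiling. It assumes that the patient removed always has the longest stay in one particular arm. A decision made on the morning of surgery could not know the stay, so a realistic effect would be smaller. If removal is unrelated to stay, one loss costs 90.2 − 88.4 = 1.8 percentage points of power. The sample size need not change. The correction is worth making mainly because it is cheap, and the pregnancy test already placed ahead of the envelope shows that a check at that point is feasible.

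**What to change.** 1. **Section 10.2.** Before the envelope step, add a signed confirmation that the criteria of 6.2 and 6.3 are still met, including pain-medication use since Visit 1. Open the envelope only if they are.
2. **Section 14.1.** Define eligible by that signed confirmation alone, so that no patient leaves the analysis on eligibility grounds once the envelope is open. Section 14 still promises a detailed SAP before the final analysis, so the definition can be repeated there.
3. **Section 8.1.** State what happens to the number of a patient who fails the check. Numbers are given at Visit 1 from a fixed list of 20, so a failure leaves an unopened envelope and, without a rule, possibly unequal arms. Either pass the unopened envelope to the next patient, or assign numbers only after the check. Say also that such a patient was never allocated and so is not a withdrawal under 12.4.

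The cost is a short form on the morning of surgery, a few sentences of text, and an occasional patient found ineligible before allocation instead of after it. The receipt-of-treatment condition in 14.1 is a separate matter that these changes leave as it is.

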STUDY DESIGN	This study is a prospective, randomized trial to compare cryoanalgesia to standard epidural analgesia for post-operative pain management in patients undergoing minimally invasive pectus excavatum repair (the Nuss procedure). 20 subjects will be randomized in 1:1 ratio to receive cryoanalgesia or epidural analgesia prior to their procedure.
PRIMARY OBJECTIVE	To compare post-operative length of stay in patients receiving cryoanalgesia vs. thoracic epidural analgesia for the Nuss procedure

SECONDARY OBJECTIVES	To compare post-operative pain scores, pain medication usage, side effects, and total cost of hospital stay in patients receiving cryoanalgesia vs. thoracic epidural analgesia for the Nuss procedure
NUMBER OF SUBJECTS	20
SUBJECT SELECTION CRITERIA	
Inclusion Criteria: Otherwise healthy male or female patients with pectus excavatum deformity, scheduled for Nuss procedure for chest wall correction, at least 13 years of age at time of Nuss procedure.
 
Exclusion Criteria:
 
 
• Age less than 13 years at time of surgery
 
• Pre-op pain medication usage
 
• Pectus carinatum
 
• Poland's syndrome or other complex chest wall anomaly
 
• Previous repair of Pectus Excavatum by any technique
 
• Previous thoracic surgery
 
• Congenital heart disease
 
• Bleeding dyscrasias
 
• History of previous problems with anesthesia or major anesthetic risk factors
 
• Pregnancy
 
• Non-English speaker
 

TEST PRODUCT, DOSE, AND ROUTE OF ADMINISTRATION	
AtriCure cryosurgical system (AtriCure, Inc., West Chester, Ohio)
 
The cryoprobe will be applied to the intercostal nerve under thoracoscopic visualization at the level of the incision and 2 interspaces above and below, bilaterally. The temperature and duration of cryoablation therapy is pre-set by the probe and cryosurgical system at 2 minutes to -60°C. Each nerve will receive one cycle of cryoablation.

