STATISTICS Primary Analysis Plan	Patient baseline characteristics will be analyzed with descriptive statistics (ie. mean age, % male, mean pectus severity index, etc.). Our primary outcome will be post-operative length of stay, which will be analyzed using a two-tailed unpaired t test, with results considered statistically significant for $p < 0.05$ . Secondary outcomes include post-operative pain scores, pain medication usage, and side effects. Pain scores will be analyzed with Mann-Whitney rank sum tests (to compare between groups at each time point) and Wilcoxon signed-rank test (to compare scores within groups over time), with results considered statistically significant for $p < 0.05$ . Pain medication usage between the two groups will be analyzed with two-tailed unpaired t test, again with results considered statistically significant for $p < 0.05$ . Given our small sample size and the low rate of complications with both analgesic methods, we expect very limited side effect data. A descriptive overall side effect rate will be calculated for each arm of the study, and the individual side effects will be listed in a table. A cost analysis will be performed, comparing the total cost of hospitalization between the cryoanalgesia and epidural groups. Difference in total cost will be assessed with two-tailed unpaired t test.

Rationale for Number of Subjects	
We used the UCSF Clinical & Translational Science Institute web-based sample size calculator (http://www.sample-size.net/sample-size-means/) to determine study size. Based on previous Nuss procedures over the past 2 years at our institution, we determined the mean length of hospitalization was 7 days, with a standard deviation of 1.3 days. From anecdotal data from our prior experience, as well as from speaking with other surgeons utilizing cryoablation, we expect patients in the cryoanalgesia group to have approximately 2 days shorter hospital stay. With type I error rate of 0.05 and type II error rate of 0.1 (yielding 90% power), our study would need 18 patients total. Allowing for some dropout, we will plan to enroll 20 patients to the study.

---	---

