#### **10.3 Visit 3- 2 weeks post-procedure**

1. Record any Adverse Experiences and Review subject diary for adverse experiences and dosing compliance.
2. Record changes to concomitant medications.
3. Perform abbreviated physical examination.
4. Perform and record vital signs.
5. Perform and record oximetry.
6. Perform post-op survey (see separate document for study tool).
7. Review pill bottles for medication usage.

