### 14.3 Analysis of Primary Endpoint

Our primary outcome will be post-operative hospital length of stay, which will be analyzed using a two-tailed unpaired t test, with results considered statistically significant for  $p < 0.05$ .

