## 14.5 Sample Size and Randomization

We used the UCSF Clinical & Translational Science Institute web-based sample size calculator (<http://www.sample-size.net/sample-size-means/>) to determine study size. Based on previous Nuss procedures over the past 2 years at our institution, we determined the mean length of hospitalization was 7 days, with a standard deviation of 1.3 days. From anecdotal data from our prior experience, as well as from speaking with other surgeons utilizing cryoablation, we expect patients in the cryoanalgesia group to have approximately 2 days shorter hospital stay. With type I error rate of 0.05 and type II error rate of 0.1 (yielding 90% power), our study would need 18 patients total. Allowing for some dropout, we will plan to enroll 20 patients to the study.

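### Adverse events are sought twice daily only while inpatient, so the overall side-effect rate may modestly favour the shorter-stay arm

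*Combined protocol and SAP*

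**What the plan says.** Section 10.2 lists the recording of adverse experiences and the inpatient survey under "Twice-per-day study visits while inpatient". Section 10.3 (2 weeks) has the investigator record adverse experiences and then "Review subject diary for adverse experiences and dosing compliance". Sections 10.4 to 10.6 repeat that item at 1 month, 3 months and 1 year. Section 4.1 times all four visits from the date of surgery, so they are common to both arms. Section 8.6 asks patients to note adverse events in a diary. Section 9.1.6 extends capture over the whole study and collects start and stop dates. Section 11.1 has the investigator ask about adverse events at every visit.

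Side effects are a secondary endpoint (Section 5.2). For their analysis the Synopsis says: "A descriptive overall side effect rate will be calculated for each arm of the study". It adds a table listing the individual effects. Section 14.4 tabulates adverse events by arm as the number of patients affected and a rate of occurrence. Neither place gives a time window, a person-time denominator or a definition of the rate.

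On length of stay, Section 14.5 states: "we determined the mean length of hospitalization was 7 days, with a standard deviation of 1.3 days", and "we expect patients in the cryoanalgesia group to have approximately 2 days shorter hospital stay".

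**The concern.** The schedule ties the intensity of enquiry to a quantity that the treatment is expected to change. A patient who goes home on day 5 is not asked again on schedule until the 2-week visit. A patient who stays to day 7 is asked about four more times in between. Minor, short-lived effects on those days are more likely to be written down for the patient still in hospital.

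If detection after discharge is less complete, the arm with the shorter stay shows a lower rate without being better tolerated. That would favour cryoanalgesia, the same direction as the trial's hypothesis. The trial is open-label once the envelope is opened (Section 8.2), and no test is planned for side effects, so readers will compare the raw rates directly. With about 10 patients per arm, one patient is 10 percentage points.

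**Working it through.** **Planning inputs.** The plan gives no figure for side-effect ascertainment. Its sample size is the only stated figure that uses the same length-of-stay inputs, so I reproduced that first. The inputs are difference 2 days, SD 1.3, two-sided alpha 0.05, power 0.90 and 1:1 allocation (Section 14.5; Section 14.3; Synopsis). With the normal approximation, n per arm = 2 × (1.96 + 1.28)² × 1.3² / 2² ≈ 8.9, rounded up to 9, or 18 in total. This agrees with "With type I error rate of 0.05 and type II error rate of 0.1 (yielding 90% power), our study would need 18 patients total". The planning stays are therefore 7 days and 7 − 2 = 5 days. I apply the historical 7 days to the epidural arm, as the plan does implicitly.

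**Scheduled adverse-event contacts.** Inpatient contacts = 2 × days of stay.

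| Period | Epidural | Cryoanalgesia | Excess |
|---|---|---|---|
| Inpatient only | 2 × 7 = 14 | 2 × 5 = 10 | 14/10 = +40% |
| Through 2-week visit | 14 + 1 = 15 | 10 + 1 = 11 | 15/11 = +36% |
| All four follow-up visits | 14 + 4 = 18 | 10 + 4 = 14 | 18/14 = +29% |
| Days 1-5 only | 10 | 10 | 0% |

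If the stay in the cryoanalgesia arm were 6 or 4 days against 7, the inpatient excess would be 14/12 = +17% or 14/8 = +75%.

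**From contacts to a recorded rate.** This step needs assumptions that the documents do not supply. Let h be a daily chance of a side effect, equal in both arms over 14 days. Let d be detection after discharge relative to inpatient detection, and L the stay. Then

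P(at least one recorded) = 1 − (1 − h)^L × (1 − h·d)^(14 − L).

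Results are epidural (L = 7) v cryoanalgesia (L = 5), with the ratio in brackets and no true difference between arms:

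| h | d = 0 | d = 0.5 | d = 0.8 | d = 1 |
|---|---|---|---|---|
| 2% | 13.2% v 9.6% (1.37) | 19.1% v 17.4% (1.10) | 22.5% v 21.8% (1.03) | 24.6% v 24.6% (1.00) |
| 5% | 30.2% v 22.6% (1.33) | 41.5% v 38.4% (1.08) | 47.5% v 46.4% (1.02) | 51.2% v 51.2% (1.00) |
| 10% | 52.2% v 41.0% (1.27) | 66.6% v 62.8% (1.06) | 73.3% v 72.1% (1.02) | 77.1% v 77.1% (1.00) |

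The largest gap in the table is 11.2 percentage points, about one patient in 10, and it requires that nothing at all is found after discharge. At d = 0.5 the gaps are 1.7 to 3.8 points, less than half a patient in 10. If all events fall within the first 5 days, the ratio is 1.00 whatever d is.

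**Is an early window equally probed?** Assume the SD of 1.3 also applies around a mean of 5 days, with a normal shape. The share of cryoanalgesia patients still inpatient at day 3 is then Φ((5 − 3)/1.3) = Φ(1.54) ≈ 94%. In the epidural arm the share is higher. A window of days 0-3 is therefore close to equal in contacts. A window to the 2-week visit is not (15 v 11).

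**The case against.** The strongest reply is that enquiry does not stop at discharge. A reader might infer from Section 10.2 that patients then rely only on a passive diary. Section 11.1 has the investigator probe at each visit, Sections 10.3 to 10.6 record adverse experiences as well as reading the diary, and the visits fall on the same dates from surgery in both arms. That stands. What remains is a difference in frequency over roughly two days, later covered by recall at 2 weeks.

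A reader might also take the 40% as excess ascertainment, or as inflation of the rate. It is neither. It counts scheduled inpatient contacts at the planning means, and even with no detection after discharge the illustrated ratios stay below 1.40.

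Other points limit the consequence. Section 1 says epidural use is limited to the first two to three post-operative days, inside both expected stays, so effects arising in that period would be probed equally. The Synopsis expects few complications and very little side-effect data, and the comparison is descriptive. Nothing confines the overall rate to the hospital stay. The survey tools are separate documents, so whether they ask about side effects cannot be judged here.

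These arguments reduce the likely size. They do not remove the dependence of enquiry on stay, and they do not supply the missing window.

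**Conclusion.** The point holds in a limited form. The frequency of adverse-event enquiry depends on the primary outcome, and the overall rate per arm has no common window to offset this. At the planned stays the epidural arm has 40% more scheduled inpatient contacts (36% through 2 weeks, 29% over all visits). The overall rate may therefore be modestly biased in favour of the shorter-stay arm.

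The documents do not support saying that the rate is biased, or by how much. That depends on event timing and on detection after discharge, and the values of h and d used above are assumptions. With half of later events detected, the spurious ratio is 1.06 to 1.10. With complete detection, or with events confined to the first 5 days, it is 1.00. The primary analysis is unaffected. This is a minor improvement to a descriptive secondary endpoint.

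**What to change.** In Section 14.4, or in the detailed SAP that Section 14 says will be written before the final analysis:

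- Keep the overall side-effect rate per arm.
- Add beside it a tabulation of side effects and adverse events by start date, in a fixed early window from surgery when nearly all patients in both arms are inpatient and equally probed, for example days 0-3. Set the window before the data are seen, and report how many patients in each arm were still inpatient at its end.
- State that later events were ascertained at an intensity that depends on length of stay.

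The cost is one extra table column, because Section 9.1.6 already collects start and stop dates. The downside is that days 0-3 largely coincide with the period of epidural infusion and leave out later effects of either method. The early window should therefore supplement the overall rate and not replace it or become the main comparison.
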